9.4.2 Safety Analyses

Analyses to decide on dose escalation will be based on safety, PK, and Pd data.

To support the decision on dose escalation, the SMC will receive results of a Bayesian dose-toxicity model, including the recommendation of next dose level from the model.

The Bayesian dose-toxicity analysis will be performed on the dose escalation set.

More details of this Bayesian two-parameter logistic regression model ([Neuenschwander et al. 2008](#)) are further specified in [Appendix 10](#).

For each SMC meeting, the model will be updated with the number of DLTs and evaluable participants per dose level. Based on the observed data the model will suggest the next dose level. The following dose levels are foreseen: 10 mg, 20 mg, 35 mg, and 50 mg. However, the SMC may decide to have different or additional dose levels or skip dose levels, except escalation may not proceed to any dose higher than 50 mg. In case escalation should proceed to doses higher than 50 mg, an amendment will be submitted.

The dose suggested by the model for the next cohort will be the dose with minimal Bayesian Risk (among all considered doses).

The target DLT toxicity for the MTD is 25%.

The SMC may choose a different dose than suggested by the Bayesian escalation approach (not higher than 50 mg). Also, the SMC may decide to change the dosing regimen as specified in Section [4.1](#). In such a case the dose toxicity model will be extended, or a separate model will be set up.

Usually decisions on dose escalation are taken once all participants of the most recent cohort have completed the DLT period or discontinued. In exceptional cases, however, the SMC may recommend on the next cohort earlier, i.e., before the last participant of a cohort has finished the DLT period (considering the available data from the current and previous cohorts as well as model recommendation). Per definition of the Dose Escalation set, participants who have not completed the DLT period are not included for update of the model, unless they experienced a DLT. However, data of such participants will be included at next SMC (if criteria for the Dose Escalation set are then fulfilled).

Before first dosing, the assumed relationship between dose level and toxicity is specified through the prior distribution. The prior distribution chosen for this study correspond to the following mean/median estimates of DLT probability:

Probability for DLT	10 mg	20 mg	35 mg	50 mg
Prior mean	15%	19%	24%	28%

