Prior median	8%	13%	18%	22%

DLT = Dose-limiting toxicity.

Details of the model, including the prior distribution can be found in [Appendix 10](#).

Decisions of the SMC in the expansion cohort will also be aided by a Bayesian two-parameter logistic regression model with the same specifications as for the dose escalation, except the prior. The prior will be based on the data seen in the monotherapy dose escalation and specified in the SMC charter before the first SMC for the expansion cohort occurs. The model will be updated at times of SMCs in the expansion cohort. Additional stopping rules in Part B apply (see Section [7.1](#)).

Other specifications are as for dose escalation and can be found in [Appendix 10](#).

Details on analyses for SMCs will be described in the SMC Integrated Analysis Plan.

All other safety analyses will be performed on the Safety Analysis population.

Endpoint	Statistical Analysis Methods
Primary (DLTs)	After end of dose escalation and main analysis, the number and proportion of participants experiencing DLTs will be reported by dose level, based on observations during the first study intervention cycle. Posterior probabilities (2.5%, 25%, 50%, 75%, and 97.5% quantiles) for DLT probabilities at selected doses will be estimated from the Bayesian logistic regression model. A sensitivity analysis will be performed using frequentist modeling (without prior).
Secondary	In general, continuous variables will be summarized using number of participants (n); mean, standard deviation; median, 25 th Percentile to 75 th Percentile (Q1-Q3), minimum, and maximum. If there are less than 5 observations available only mean and the observed data will be given. Categorical variables will be summarized using frequency counts and percentages. The calculation of proportions will be based on the number of participants in the analysis set of interest, unless otherwise specified in the study Integrated Analysis Plan. Details will be specified in the Integrated Analysis Plan finalized before database lock.
Tertiary/Exploratory	Details will be specified in the Integrated Analysis Plan finalized before database lock.

DLT = Dose-limiting toxicity.

QT/QTc Analysis

The ECG parameter will be summarized by descriptive statistics per time point; changes from Baseline will be calculated.

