Appendix 10 Description of the Bayesian Dose Escalation Model

The Bayesian model is based on the number of DLTs and evaluable participants per dose level. The SMC will receive results of a Bayesian two-parameter logistic regression model updated with the observed DLT data (Neuenschwander et al. 2008), including a recommendation for the next dose. For a dose level d_j , the relationship between dose and probability of toxicity P (DLT) is defined by:

$$P(DLT|d_j, \alpha, \beta) = \frac{\exp\left(\alpha + \exp(\beta) * \log\left(\frac{d_j}{d_{ref}}\right)\right)}{1 + \exp\left(\alpha + \exp(\beta) * \log\left(\frac{d_j}{d_{ref}}\right)\right)},$$

with bivariate normally distributed parameters (α, β) using the following parameterization:

- preselected dose level $d_j \in \{10 \text{ mg}, 20 \text{ mg}, 35 \text{ mg}, 50 \text{ mg}\}$ subject to change by SMC)
- Reference dose $d_{ref} = 90 \text{ mg}$
- $E(\alpha) = -0.708$, $E(\beta) = -0.389$
- $SD(\alpha) = 1.2$, $SD(\beta) = 0.9$, $Cov(\alpha, \beta) = 0$.

The target DLT toxicity is 25%. The following toxicity regions for use in dose suggestion will be defined:

Toxicity Intervals	Probability of DLT	Loss term (weight in loss function)
Under-Dosing	[0.0, 0.20]	1
Targeted toxicity	(0.20, 0.35]	0
Excessive toxicity	(0.35, 0.60]	2
Unacceptable toxicity	(0.60, 1.00]	3

Recommendation on the next dose level by the model is determined as follows:

- Select the dose level that minimizes the loss function. The loss function is defined as the sum of products of the probability to lie within each of the toxicity regions, and the associated loss term:

$$1 \times P(\text{under-dosing}) + 0 \times P(\text{targeted toxicity}) + 2 \times P(\text{excessive toxicity}) + 3 \times P(\text{unacceptable toxicity}).$$

The model will be provided with the following preselected dose levels: 10 mg, 20 mg, 35 mg and 50 mg. The set of doses can be changed any time by the SMC.

The SMC will be notified of a potential candidate dose for MTD once

- the upper bound of the 95% credible interval of a potential MTD is not more than 40% and the estimated DLT probability for the suggested MTD is above or equal to 17%.

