15.1 DLT analysis

Of Note, DLT as per SMC decision will be available in the table “Review of data” in the SMC minutes.

In case of new DLT appears after DLT period, the minutes will be updated.

A table will display the following (per regimen and dose level and in total) for the DLT analysis set:

- Number and percentage of participants with a DLT per investigator's judgement as recorded in eCRF (using DLT flag from the AE CRF page)

Number and percentage of participants with a DLT per SMC decision

A listing of DLTs (per investigator and/or per SMC) will be provided by dose level and participant, including whether it was judged to be a DLT by investigator and/or by SMC

This listing will additionally contain age, sex, type of myeloma, SOC, PT, grade, SAE (yes/no), relatedness to M3258 (yes/no), start date (+treatment day), stop date (+treatment day), action taken with M3258, if treatment was stopped before start of AE: days since stop of treatment, and outcome.

In addition, the following will be presented:

- Quantiles (2.5%, 25%, 50%, 75% and 97.5%) for the posterior probability of a participant experiencing a DLT at each of the dose levels used in the study according to the same Bayesian Logistic Model (BLM) as described in the SMC IAP (see [Appendix 18.1](#)) or

SMC charter (if change occurred). For this analysis either SAS or R (using the package bcrm or crmPack) will be used.

MTD suggestion from the Bayesian logistic regression model

The MTD as suggested from the modeling will be derived as follows:

- 1) The BLRM will be updated with all DLT data (SMC decision) from the dose escalation.
- 2) The dose with targeted toxicity probability of 25% will be identified.
- 3) The next lower tested dose with the upper bound of the 95% credible interval of a potential MTD below or equal 40% and with estimated DLT probability above or equal to 17% will be selected.
- 4) The credibility interval will be provided.
- 5) If the MTD estimate of all tested doses is below 17%, there is no MTD suggestion from the model.

This information will be forwarded to the SMC that will decide on the determination of the MTD.

Additionally, the SMC will receive the estimated DLT probability and associated probability quantiles for all other doses tested.

For above analysis either SAS or R (using the package bcrm or crmPack) will be used.

Frequentist MTD suggestion

As second approach, the MTD as suggested by the frequentist estimation will also be derived:

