- 1) All DLT data from the dose escalation will be included in a two-parameter logistic regression model (intercept and slope over log of the scaled dose, no prior; if the model does not converge, it will be reported as not calculable; the program code for this analysis can be found in the TLF shells).
- 2) The dose with targeted toxicity probability of 25% will be identified.
- 3) The next lower tested dose will be selected.

The two-sided confidence interval for the DLT probability will be provided.

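### The frequentist MTD suggestion in SAP 15.1 has no rule for a fitted slope that is not positive, so it can name a dose that its own fit puts above the 25% target, or find no dose to name

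*SAP*

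**What the plan says.** Protocol 9.4.2 attaches this analysis to the primary DLT endpoint: "A sensitivity analysis will be performed using frequentist modeling (without prior").

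SAP 15.1, under the frequentist MTD suggestion, sets three steps:

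1. Fit all dose-escalation DLT data with a "two-parameter logistic regression model (intercept and slope over log of the scaled dose, no prior; if the model does not converge", the result is reported as not calculable). A note adds that "the program code for this analysis can be found in the TLF shells".
2. Find where the fitted curve reaches a DLT probability of 25%.
3. Apply the selection rule: "The next lower tested dose will be selected".

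A two-sided confidence interval for the DLT probability is to be given.

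The Bayesian counterpart differs in two ways. Protocol Appendix 10 multiplies log dose by exp(beta), "with bivariate normally distributed parameters" alpha and beta, so its slope is always positive. SAP 15.1 also screens the dose that the Bayesian model selects: "The next lower tested dose with the upper bound of the 95% credible interval of a potential MTD below or equal 40" percent and an estimated DLT probability of at least 17%. It makes no suggestion if the estimates at all tested doses are below 17%. The frequentist steps contain no such screen and no branch for making no suggestion, other than non-convergence.

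**The concern.** An unpenalised logistic fit to a handful of participants per dose can show toxicity falling with dose purely by chance, and it converges normally when it does. The non-convergence exception is then not triggered. Steps 2 and 3 assume a rising curve, on which a lower dose is a safer dose. On a falling curve, the next lower tested dose is a more toxic one according to the fit itself.

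The study report could therefore show a frequentist MTD that contradicts the model it came from. A reader would see what looks like disagreement with the Bayesian result, when the cause is a gap in the rule. The text also does not say what to report when no tested dose lies below the fitted 25% dose.

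**Working it through.** **Inputs.** Doses: "The following dose levels are foreseen: 10 mg, 20 mg, 35 mg, and 50 mg" (Protocol 9.4.2). Anticipated sizes: two levels of 3 and two of 6, 18 in total (Protocol 9.2, which does not say which doses get 6). True DLT rates: the protocol's prior medians 8/13/18/22% and prior means 15/19/24/28%. Target: 25%.

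**The plan's own figures.** Drawing 1,000,000 values from the Appendix 10 prior (alpha mean -0.708, SD 1.2; beta mean -0.389, SD 0.9; reference dose 90 mg) gives means of 14.7/18.8/23.4/27.4% and medians of 7.9/12.3/17.5/22.1%. All are within 1 point of the protocol's table. The documents state no frequency of negative slopes.

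**Algebra.** With logit P(d) = a + b·log(d/90), the 25% dose is d25 = 90·exp[(log(1/3) - a)/b]. For any dose d, logit P(d) - logit(0.25) = b·log(d/d25). If b < 0 and d < d25, both factors are negative and the product is positive, so P(d) > 25%. This holds for any choice of scaling dose.

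**Example 1.** DLTs 1/3, 1/3, 1/6, 1/6 give a = -2.057 and b = -0.677.
- d25 = 90·exp[(-1.099 + 2.057)/(-0.677)] = 21.9 mg.
- Fitted rates are 36.2/26.2/19.5/16.0%.
- The rule names 20 mg (26.2%), although the fitted rates at 35 and 50 mg are lower.

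**Example 2.** DLTs 1/3, 0/3, 1/6, 1/6 give a = -2.086, b = -0.407 and d25 = 7.9 mg. No tested dose lies below it.

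**Frequency.** For fixed groups, every possible DLT outcome was enumerated and fitted by maximum likelihood. Data with no DLTs, or with complete or quasi-complete separation, were counted as not calculable. The other rows are simulations of 2,000 to 8,000 trials each. Cells show prior-median rates / prior-mean rates, as a share of all trials.

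| Dose assignment | Slope negative | Slope negative and a dose named |
|---|---|---|
| Fixed 3/3/6/6 | 20.8% / 27.5% | 11.5% / 20.7% |
| Fixed 6/6/3/3 | 23.8% / 28.6% | 5.7% / 15.0% |
| Minimum-loss model, no skipping, 6 cohorts of 3 | 7.7% / 5.5% | about 0% / about 0% |
| 3+3 | 5.9% / 3.9% | about 0% / about 0% |
| Up on 0 DLTs, stay on 1, down on 2 or more | 10.9% / 11.7% | 1.0% / 4.0% |
| Up on 0 or 1 DLT, down on 2 or more | 16.5% / 21.0% | 7.9% / 13.9% |

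With a steeper assumed curve (5/12/25/40%) and fixed 3/3/6/6, slopes are negative in 5.7% of trials and a dose is named in 3.5%.

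**After the early stop.** SAP 14.2 names only 10 mg QD, 10 mg BIW and 20 mg BIW. Suppose the fit uses 10 and 20 mg alone. The two-parameter model then reproduces the observed rates, and the slope is negative when the rate at 10 mg exceeds that at 20 mg. Summing binomial products over outcomes with both DLTs and non-DLTs at each dose, a negative slope with a dose named occurs in 0.5% / 2.1% (3+3) and 3.1% / 10.0% (6+6) of trials. It reaches 17.0% for 3+6 at prior means. These group sizes are assumed.

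**The case against.** A reader might infer from the fixed-group figures that about one trial in four would report an MTD above target. The documents do not support that, for two reasons. Escalation is adaptive: the minimum-loss model informs the SMC, which may depart from it, and 3+3+6+6 is only an anticipated scenario. In addition, a negative slope is not the same event as naming a dose above target. Even with fixed groups, only 24% (5.7/23.8) to 75% (20.7/27.5) of inverted fits name a dose. Under the minimum-loss rule almost none do.

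A reader might also infer that a dosing decision rests on this result. It does not. The study is descriptive, the SMC determines the MTD, and SAP section 7 records that the study stopped before Part A met its objective and before Part B began. The planned confidence interval would also give a reader some sight of the estimate.

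The program code sits in TLF shells that are not among the documents, so a check on the sign of the slope cannot be excluded.

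All of this limits frequency and weight. None of it supplies the missing rule. The SAP itself says when the result is not calculable and lists only non-convergence, and the analysis remains specified in the version adapted to the early stop. Under the minimum-loss rule the usual result of an inverted fit is that no tested dose lies below the 25% dose, and the text does not cover that either.

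**Conclusion.** Wrong as written, low impact. That a named dose has a fitted rate above 25% whenever the slope is negative follows from the algebra and needs no simulation.

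The frequency cannot be given as one number. Negative slopes occur in 20.8% to 27.5% of trials for fixed 3/3/6/6 groups at the plan's prior rates, and in about 5-8% under the protocol's minimum-loss rule. A dose above target is named in 11.5% to 20.7% and in almost none, respectively.

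These figures assume that:
- true rates equal the prior medians or means;
- separated data count as non-converged;
- the SMC follows the stated rule in each simulation.

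The frequentist step does not say whether QD and BIW data are pooled, so the trial's actual configuration was not modelled beyond the two-dose illustration.

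**What to change.** Add to step 1 or step 3 of the frequentist MTD suggestion: *If the estimated slope is zero or negative, the data are separated, or no tested dose lies below the estimated 25% dose, the frequentist MTD is reported as not calculable.* Report the fitted DLT rate at any dose that is selected.

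Forcing a positive slope through exp(b), as in the Bayesian model, is not a substitute. When the free slope is negative, that likelihood has no interior maximum: b runs to minus infinity, the curve goes flat and no 25% dose can be estimated.

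The cost is one sentence and a small change to the program. The downside is that more trials report no frequentist MTD. For fixed 3/3/6/6, removing the negative slopes cuts the calculable share from about 93% to 66% (93.1 - 27.5) at prior means and from about 83% to 63% (83.4 - 20.8) at prior medians. Under the minimum-loss rule it falls by at least 5.5 points from about 61%, and by at least 7.7 points from about 58%. Fits with a slope of exactly zero or with no tested dose below the 25% dose reduce it slightly further. For a descriptive sensitivity analysis that is acceptable.

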15.2 Adverse Events

AEs will be analyzed among the SAF analysis set and presented by regimen and dose (in increasing order) and summarized. Only participants counts will be presented with frequency.

Treatment-emergent adverse events (TEAE) are those events with onset dates occurring within the on-treatment periods as defined in section [9.4](#).

- **Related Adverse Events:** AEs with relationship missing, unknown or yes. Relationship is judged separately for M3258, and dexamethasone.
- **SAEs:** Serious adverse events (as recorded on the AE eCRF page, Serious Adverse Event = 'Yes').
- **AEs Leading to Treatment Discontinuation:** AEs leading to permanent discontinuation of study treatment (as recorded on the AE eCRF page, Action taken with study treatment = 'Drug withdrawn'). Treatment discontinuation is recorded separately for M3258, and dexamethasone.
- **AEs Leading to Death:** AEs leading to death (as recorded on the AE eCRF page, Outcome = 'Fatal').

All analyses described in Section [15.2](#) will be based on TEAEs if not otherwise specified.

TEAEs will be summarized by number and percentage of participants with at least one TEAE in the category of interest, by primary MedDRA and PT (both sorted alphabetically), unless otherwise stated. Each participant will be counted only once within each SOC or PT. If a participant experiences more than one AE within a SOC or PT for the same summary period, only the AE with the strongest relationship or the worst severity, as appropriate, will be included in the summaries of relationship and severity.

The severity of adverse events will be graded using the NCI-CTCAE version 5.0, except where CTCAE grades are missing. No imputation of missing grades will be performed.

Adverse events will be coded according to the latest MedDRA version at the time of the data cut-off.

Incomplete AE-related dates will be handled as defined in section [9.5](#).

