
 To determine safety, tolerability and the MTD (if observed) of M3258 as a single agent in participants with RRMM 	
 Occurrence of DLTs in participants with RRMM receiving M3258 as a single agent during the DLT period Occurrence of any AEs reported (serious or nonserious) will be considered TEAEs and TRAEs (including TEAEs leading to death or discontinuation of treatment) in participants receiving M3258 as a single agent from start of study intervention to 30 days after End of Study Intervention Occurrence of TEAEs outside of the DLT period that SMC deems relevant for determination of the MTD Study treatment-emergent changes in clinical laboratory measures from Baseline, safety ECGs measures, vital signs, ECOG performance status in participants receiving M3258 as a single agent from start of study intervention to 30 days after end of study intervention
Secondary	

 To investigate the PK profile of M3258 (single and multiple dose exposure) in participants with RRMM 	
 PK profile of M3258 in terms of C_{max}, AUC_{0-t}, AUC_{0-24} at Day 1, Cycle 1, (single dose): predose, 1, 2, 3, 4, 5, 6, 8 and 24 h after administration PK profile of M3258 in terms of C_{max}, AUC_{0-24} at Day 8 Cycle 1, (multiple dose): predose, 1, 2, 3, 4, 5, 6, and 8 h after administration

 To investigate the recommended dose and regimen for expansion (RDE) in participants with RRMM 	
 In addition to safety, tolerability and PK, for selection of recommended dose and regimen for expansion (RDE), changes in Pd (LMP7 activity) in pre and post study intervention samples on Day 1 Cycle 1 pre and postdose, Day 2 Cycle 1 predose and Day 8 Cycle 1 pre and postdose

Objectives	Endpoints (Outcome Measures)
	
 Changes from Baseline in serum M-protein, urine M-protein, or free light chain protein levels (for free light chain disease) on Day 1 of every cycle

 To evaluate preliminary clinical activity using IMWG criteria 	
 OR, DOR, Time to Response until CR, sCR, VGPR or PR according to IMWG
Exploratory	

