4.1 Overall Design

This is a Phase I, open-label, FiH, 2-part (dose escalation and expansion), noncontrolled, multicenter clinical study designed to determine the safety, tolerability, PK, Pd and early signs of efficacy of M3258 as a single agent and co-administered with dexamethasone in participants with RRMM whose disease has progressed following > 3 prior lines of therapy and for whom no effective standard therapy exists (Figure 1).

The dose escalation phase is aimed at determining the recommended dose and regimen for the expansion phase (RDE) and the MTD based on safety, tolerability, PK, Pd (including LPM7 activity) and initial efficacy data of M3258 as a single agent. Following the dose-escalation phase, the safety and tolerability of M3258 with dexamethasone will be investigated in an expansion cohort of approximately 30 participants in addition to assessment of early clinical activity. If the dose is modified during the expansion phase, this sample size will increase by approximately 3-21 participants.

Each phase of the study will include a Screening period of up to 28 days, a study intervention period consisting of 21- or 28-day cycles of either M3258 alone (Part A) or M3258 in combination with dexamethasone (Part B), an End of Study Intervention visit (within 7 ± 3 days), and a Safety Follow-Up period of 30 (± 7) days. In Part B, participants will be followed up until 6 months after the last-participant-last-study-intervention intake. Participants who tolerate M3258 \pm combination with dexamethasone without significant clinically relevant toxicities may continue to receive their assigned dose if there is no evidence of confirmed disease progression (Section 4.4). Participants who discontinue study intervention for any reason will complete the End of Study Intervention and Safety Follow-Up visits.

Screening Period

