8.3 Adverse Events and Serious Adverse Events

The definitions of an AE and a SAE are in [Appendix 5](#).

8.3.1 Time Period and Frequency for Collecting Adverse Event and Serious Adverse Event Information

The AE reporting period for safety surveillance begins when the participant is initially included in the study (date of first signature of informed consent/date of first signature of first informed consent) and continues until the 30-Day Follow-Up Safety Visit.

Any SAE assessed as related to study intervention must be recorded and reported, as indicated in [Appendix 5](#), whenever it occurs, irrespective of the time elapsed since the last administration of study intervention.

The method of recording, evaluating, and assessing causality of AEs (including SAEs) and the procedures for completing and transmitting SAE reports are in [Appendix 5](#).

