Elective hospitalization to observe, administer or simplify study intervention or study procedure (for instance, an overnight stay to facilitate chemotherapy and related hydration therapy application) are not considered SAEs. However, all events leading to unplanned hospitalizations or unplanned prolongation of an elective hospitalization (i.e., undesirable effects of any administered treatment) must be documented and reported as SAE.

Events Not to Be Considered as AEs/SAEs

Medical conditions present at the initial study visit that do not worsen in severity or frequency during the study are defined as Baseline Medical Conditions and are not to be considered AEs.

AE/SAEs Observed in Association with Disease Progression

Progression of the disease/disorder being studied assessed by measurement of lesions on radiographs or other methods as well as associated clinical signs or symptoms (including laboratory abnormalities) should not be reported as an (S)AE, unless the participant's general condition is more severe than expected for the participant's condition and/or unless the outcome is fatal within the adverse event reporting period, as defined in Section 8.3.2.

Adverse Events of Special Interest

Based on theoretical safety concerns related to a M3258, Investigator should report AESIs (Section 6.9) to the Sponsor in an expedited manner, regardless if they satisfy the standard definition of an SAE. AEs of special interest for monitoring are then reported following the procedure for an SAE specified below for reporting SAEs, AESI, and DLTs.

Recording and Follow-Up of AE and/or SAE

At each study visit, the participant will be queried on changes in his or her condition. During the reporting period, any unfavorable changes in the participant's condition will be recorded as AEs, whether reported by the participant or observed by the Investigator.

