9.4 Definition of On-treatment Period

The on-treatment period is defined as the time from first dose of study intervention to 30 days after end of study intervention, or the cut-off date, whichever occurs first.

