15.3 Adverse Events

The severity of adverse events will be graded using the NCI-CTCAE version 5.0, except where CTCAE grades are missing. No imputation of missing grades will be performed. Adverse events will be coded according to the latest MedDRA version at the time of the data cut-off.

- **TEAEs:** Any AEs that are reported (serious and non-serious) will be considered treatment emergent adverse events (TEAEs), with the exception of those that started prior to the first dose of study treatment (unless a worsening of the event is recorded after the first dosing, in which case the event will be counted as a TEAE), or AEs starting more than 30 days after the last dose of study treatment.
- **Related Adverse Events:** AEs with relationship missing, unknown or yes. Relationship is judged separately for M3258, and dexamethasone.
- **SAEs:** Serious adverse events (as recorded on the AE eCRF page, Serious Adverse Event = 'Yes').
- **AEs Leading to Treatment Discontinuation:** AEs leading to permanent discontinuation of study treatment (as recorded on the AE eCRF page, Action taken with study treatment = 'Drug withdrawn'). Treatment discontinuation is recorded separately for M3258, and dexamethasone.
- **AEs Leading to Death:** AEs leading to death (as recorded on the AE eCRF page, Outcome = 'Fatal').

AEs will be summarized by MedDRA PT as event category and MedDRA primary SOC as summary category. In general, each subject will be counted only once within each PT or SOC.

AEs with missing classifications regarding relationship to study treatment, and those with start date on or after the start of study treatment, will be considered as related to the study treatment.

Missing data handling

Incomplete AE-related dates will be handled as follows:

CCI

CONFIDENTIAL
INFORMATION

20/38

M3258

First in Human Dose Escalation of M3258 as a Single Agent and Expansion Study of M3258 in Combination with Dexamethasone

MS201814-0010

Version 2.0

- If the onset date is missing completely or missing partially – but the onset month and year, or year, are equal to that of the study treatment start – then the onset date will be replaced by the minimum of the start of study treatment and the AE resolution date.
- In all other cases, the missing onset day or month will be replaced by 1.

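### The main SAP's TEAE definition leaves out pre-dose events that worsen after dosing, while the appended SMC plan counts them; the difference is undeclared and could remove some events from the TEAE tables

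*SAP*

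**What the plan says.** The main SAP and the SMC plan in its Appendix 18.1 each define a TEAE.

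- **Main SAP, Section 15.2:** "Treatment-emergent adverse events (TEAE) are those events with onset dates occurring within the on-treatment periods". Section 9.4 fixes the period: "The on-treatment period is defined as the time from first dose of study intervention to 30 days after end of study intervention". An earlier data cut-off ends it sooner. There is no clause on worsening. All Section 15.2 analyses "will be based on TEAEs if not otherwise specified".
- **SMC plan, Section 15.3:** events that started before the first dose are excluded "unless a worsening of the event is recorded after the first dosing, in which case the event will be counted as a TEAE". Events starting more than 30 days after the last dose are excluded as well.

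The protocol does not decide between them. For the Part A primary objective, Protocol Section 3 (Table 7) says: "Occurrence of any AEs reported (serious or nonserious) will be considered TEAEs and TRAEs". It gives the window from the start of study intervention to 30 days after its end, but does not address an event that is present before dosing and then worsens.

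On collection, Protocol 8.3.1 says: "The AE reporting period for safety surveillance begins when the participant is initially included in the study", meaning the date of first consent. Protocol 4.1 adds: "Each phase of the study will include a Screening period of up to 28 days". Protocol Appendix 5 leaves detailed recording guidance to CRF completion conventions that are not part of these documents.

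SAP Section 7 reports the early stop, the altered DLT set, the extension of β5c analyses to Part A, and the handling of participants dosed above plan. It does not mention the TEAE definition.

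**The concern.** Both definitions are current text in one document, and they can classify the same event differently. TEAE and TRAE occurrence is one component of the Part A primary endpoint. The narrower rule governs the Section 15.2.1 summary tables (all, related, Grade 3 or higher, Grade 4 or higher, serious, fatal, leading to discontinuation), the worst-toxicity table and the table prepared for the public registries. It also governs the Section 15.2.2 listing, which covers only TEAEs that led to stopping, interrupting or reducing the drug.

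At stake is an event that began between consent and first dose, worsened on drug, and perhaps led to a dose change. It could be missing from these outputs although the SMC's TEAE tables, built on the broader rule, would count it.

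**Working it through.** The plan gives no figure to reproduce. The check sets the two definitions side by side and then bounds the effect on a table row.

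**Step 1: classify one event.** Let an AE start at time S, the first dose be at D, and a worsening occur at W within 30 days of the last dose and before any cut-off, with S < D < W. Such an event can exist because AEs are collected from consent and screening lasts up to 28 days.

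| How the eCRF holds the worsening | Main SAP 15.2 | SMC plan 15.3 |
|---|---|---|
| Same record, onset date stays S | S is before D: not a TEAE | Worsening recorded after D: TEAE |
| New record, onset date W | W is on treatment: TEAE | TEAE |

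The definitions diverge only in the first row. Nothing in the documents says which row applies.

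**Step 2: who is exposed.** Under Protocol Appendix 5, conditions present at the initial visit "that do not worsen in severity or frequency during the study" are baseline conditions and not AEs. A baseline condition that worsens on treatment becomes an AE, plausibly with an on-treatment onset, and both definitions would then count it. The exposed group is mainly AEs that first appear between consent and first dose.

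**Step 3: which outputs change.**

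- Affected: the Section 15.2.1 TEAE and TRAE tables and the Section 15.2.2 listing.
- Not affected: the listing of all AEs and the listing of Grade 3 or higher events, which expressly includes non-TEAEs (15.2.1); the SAE listing, which flags onset outside the on-treatment period (15.3.2); the DLT tables, which use the investigator's flag and the SMC's decision (15.1); and the laboratory shift tables, which compare baseline grade with worst on-treatment grade (15.4).

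**Step 4: largest change in one row.** SAP Section 9 takes percentages over the analysis set, and Section 15.2 counts each participant once per SOC or PT. If n is the group size, moving one participant changes a row by at most 100 × 1/n points. Protocol 9.2 anticipates two dose levels of 3 and two of 6, 18 in all, and allows 3 to 9 per level.

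- n = 3: 100 × 1/3 = 33.3 points
- n = 6: 100 × 1/6 = 16.7 points
- n = 9: 100 × 1/9 = 11.1 points
- n = 18 (all of Part A): 100 × 1/18 = 5.6 points

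These are planned sizes. The study stopped early for lack of enrolment, and the documents do not give the actual sizes. A row changes only if the participant has no other event qualifying for it, so preferred-term and high-grade rows are more exposed than the any-TEAE row.

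**The case against.** The strongest reply is that the consequence rests on an unseen document. If the CRF conventions require a new AE record for each worsening, both definitions give the same counts. One might infer from the SMC plan's explicit clause that worsening is kept on the original record. That does not follow, because a recorded worsening can be either a new record or a changed grade. This part of the objection stands, and the point has to be stated conditionally.

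A reader might also infer that worsening of long-standing cytopenias or neuropathy would be lost. The documents do not support that. Worsened baseline conditions become AEs in their own right. Laboratory worsening appears in the shift tables, the Grade 3 or higher laboratory listing and the hematology line plots whatever the TEAE status. Neuropathy that worsens by two grades or reaches Grade 3 in the DLT period meets a DLT criterion.

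The all-AE listing is a real safeguard: the events are not lost from the report. It is only partial, because its specified fields include grade, start date and stop date but no flag or date for worsening. A reader could not reliably pick out which pre-dose events worsened on drug, and incidence is read from the summary tables.

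Finally, all analyses are descriptive, and the study stopped before Part A met its primary objective. That lowers the stakes but does not remove the conflict between the two definitions.

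**Conclusion.** The inconsistency is real and undeclared, and Section 15.2 should be changed. If worsening stays on the original record, an AE that began between consent and first dose and worsened on treatment is a TEAE for the SMC but absent from the report's TEAE and TRAE tables and from the Section 15.2.2 listing. It remains in the all-AE listing and, if Grade 3 or higher, in that listing too.

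The number of such events cannot be derived from the documents and may be zero. The per-row maximum is 33 points in a planned group of 3 and 17 points in a planned group of 6, under the condition in Step 4.

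It would go too far to say that the report will undercount the primary safety endpoint. Only its TEAE and TRAE component is exposed, and only under a recording practice that the documents neither confirm nor exclude. Nor are 17 to 33 points the effect of any one event; they are an upper bound for a single row.

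**What to change.** Use one TEAE definition in both plans. Amend SAP Section 15.2 so that a TEAE is an AE whose onset falls in the Section 9.4 on-treatment period, or an AE with onset before the first dose for which a worsening is recorded after the first dose.

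If a time limit on the worsening is wanted, require it to fall within the Section 9.4 period and present that as new wording. The SMC plan sets no time limit on the worsening and does not say that it must be in grade.

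State in the same section how the eCRF records a worsening.

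The cost is about one sentence and a small programming check. If worsening always creates a new AE record, no result changes. If the eCRF keeps a single grade per record with no date of worsening, the clause cannot be programmed from that record alone, and the check will show this before database lock.
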